	13.	Comfortable with the use of a smartphone. If assistance is required for the use of FeetMe technology, a caregiver or volunteer is fully available to assist the patient.
	14.	Willingness to be regularly contacted via phone-calls.
	15.	Willingness to suspend conventional physiotherapy treatment and start the FeetMe rehabilitation program, if applicable.
	16.	French speaker.
	Pat	ients must not fulfil the following criteria:
	Exe	clusion criteria
	1.	Medical history indicating a Parkinsonian syndrome other than idiopathic PD.
	2.	Unable to walk without walking aid or presence of an injury preventing the patient to walk.
	3.	Any relevant comorbidity or vestibular/visual dysfunctions limiting locomotion or balance.
	4.	Clinically significant comorbidities which in the judgement of the investigator may preclude the reliable gait assessment of the patient.
	5.	Patients with poor wound healing or broken skin on the feet.
	6.	Patients with foot implants.
	7.	Montreal Cognitive Assessment (MoCA) score $\leq 24/30$.
	8.	Patients with dementia.
	9.	Patients with apathy.

	10. Participation in another clinical trial with an investigational drug/ therapeutic within the three months before screening and during the study, unless agreed by the Sponsor.
	11. Patients who had Lee Silverman Voice Treatment (LSVT) Big therapy within the past 12 months or have it planned during the course of the study.
	12. Patients with Deep Brain Stimulation planned during the first 12 weeks of the study.
	13. Patients with pacemakers.
	14. Patients performing vigorous exercise > three times a week, 30 mins or more per session.
STUDY DESIGN AND ASSESSMENTS	This is a multicentre, controlled, randomised in two parallel-groups, open-label, study designed to evaluate the efficacy of FeetMe home- based self-rehabilitation program in comparison to conventional physiotherapy, including no physiotherapy in patients with PD. The study consists of a screening period, a primary intervention period of 12 weeks and a long-term intervention period of 12 weeks.
	Screening

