4.5 Conventional physiotherapy

The control arm in the study consists of patients who have a prescription for conventional physiotherapy and did not get randomised into the FeetMe arm. Their rehabilitation should typically follow the HAS recommendations nevertheless, in order to make this group the most representative of real life the protocol will not standardise what is performed as part of the conventional physiotherapy. Patients who have no access to physiotherapy despite having a prescription will therefore also be part of the conventional physiotherapy arm.

The only restrictions are the ones specified in the eligibility criteria for both arms, i.e.: patients who had LSVT Big therapy within the past 12 months or are scheduled to have it during the course of the study or patients performing vigorous exercise more than 3 times a week, 30 mins or more per session either as part of their rehabilitation or otherwise, are excluded.

Patients will be asked to track their conventional physiotherapy using the weekly diary in Appendix F so the method and the time spent on rehabilitation can be evaluated and compared for analysis.

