- provide the opportunity to those patients on the conventional physiotherapy arm who will not find a therapist during the study to get access to treatment by switching to FeetMe;
- assess the ratio of the willingness to continue on the FeetMe arm in comparison to the conventional arm;
- assess the maintenance of the treatment effect in patients who decide to stop;
- compare efficacy of the two treatment within the same individual who decides to switch;
- compare the long-term efficacy of the two treatments at 6 month in patients who continue on their original allocation.

Based on the emerging data, the Sponsor may decide to open an extension phase, where all participants have the option to take part or prolong their participation in the FeetMe rehabilitation program. Such extension to this study may be offered to all patients, contingent on the Sponsor's decision to implement it and could be described in a separate document.

In case study conduct will be compromised by the COVID-19 pandemic a contingency plan will be provided in a clinical investigational plan addendum.

FeetMe reserves the right to temporarily suspend or prematurely discontinue the study at any time. The study may also be terminated prematurely at any time when agreed by both the Investigators and the Sponsor as being in the best interest of the patients. In terminating the study, FeetMe and the Investigator will ensure that adequate consideration is given to the protection of the patients' interests. If the study is prematurely terminated or suspended, FeetMe will inform the Investigators/institution and the regulatory authorities and IEC in accordance with applicable regulatory requirements. In addition, arrangements will be made for the return of all study material provided by the Sponsor.

CIP Number 2023-A00150-45 Final version 0.2

CONFIDENTIAL May 2023

Figure 3. Schematic of the study design

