7.4 Primary Intervention Period

Following the Baseline Visit, all patients will begin their 12-week physiotherapy (or no-physiotherapy) regimen according to their randomisation.

During this period:

- All patients will participate in the Remote Gait Monitoring 1 and Visits 1-3 (Sections 7.3.1, 7.3.2, 7.3.3).
- Patients on the Conventional Physiotherapy arm, if they have access to it will start or continue their conventional physiotherapy and will keep track of it using the Conventional Physiotherapy Tracking Sheet (Appendix F). Patients who did not have access to CPt at the time of inclusion but manage to arrange one during the Primary Intervention Period will restart their PIP.
- On the other arm patients will start the FeetMe rehabilitation program (Section 4.4, Appendix A and B).
- In addition, all patients will keep a falls diary (Appendix G).

7.4.1 Remote Gait Monitoring 1

At the end of the Baseline Visit, all patients will take the FeetMe Insoles, mobile devices and chargers with them to their homes. A Patient User Guide will be provided.

- All patients will use the insoles remotely while performing their day-to-day activities (including physiotherapy) for two weeks. Data will be recorded in standalone mode (without a phone).
- Patients will download the data from the insoles at the end of each day.

7.4.2 Visits 1 and 2

Four and eight weeks after Baseline Visit, two remote visits (Visit 1 and 2) will take place. Patients will be asked to fill in the following questionnaires:

- PDSS-2
- Pain VAS
- Parkinson Disease Questionnaire, Short Form (PDQ-8).

7.4.3 Visit 3

Twelve weeks after Baseline Visit, that is, at the end of the 12-week Primary Intervention Period, all patients will participate in an in-clinic visit (Visit 3), where they will perform the same series of assessments as in the Baseline Visit. Patients will need to bring their FeetMe devices, their diaries, trackers and filled-in questionnaires to the visit.

The following assessments will be performed at Visit 3:

- Gait Assessments, which must be performed in the ON-phase:
 - 6 Minutes Walk Tests (6MWT)
 - Mini-BESTest.

During the 6MWT and the Mini-BESTest patients must wear the insoles. Specific instructions set out in the Site User Manual must be followed when setting up and executing the assessments.

- Disease specific rating scales:
 - MDS-UPDRS
- Other Assessments:
 - FOG-Q
 - PDSS2
 - Pain VAS
 - PDQ39

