9.1 Analysis sets

The Screened set includes all subjects for whom informed consent to participate in the study was obtained and have a subject identification number.

The Full Analysis Set (FAS) includes all subjects randomised to one of the pre-defined treatment arms and who had a baseline gait measurement.

No Per Protocol Set (PPS) is planned to be defined for this study.

The Safety Set (SAF) includes all subjects who were randomised, removing only patients who do not start their assigned therapy.

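### The Safety Set rule conflicts with the control-arm definition: read literally, it drops controls who never get physiotherapy although they wear the study insoles

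*Protocol*

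**What the plan says.** Section 9.1 (Analysis sets) defines the set in one sentence, as every randomised patient, "removing only patients who do not start their assigned therapy". Section 9.2.7 uses this set for every safety analysis. Table 9.1 in section 9.1.1 applies it to both randomised groups and labels the control group simply as conventional physiotherapy.

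The control arm is described more broadly elsewhere:

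- The synopsis gives the comparator as conventional "physiotherapy, including no physiotherapy in patients with PD".
- Section 4.5: "Patients who have no access to physiotherapy despite having a prescription will therefore also be part of the conventional physiotherapy arm".
- Section 6.1 offers the Week 12 switch partly for the benefit of "those patients on the conventional physiotherapy arm who will not find a therapist during the study".
- Section 7.4: "Patients on the Conventional Physiotherapy arm, if they have access to it will start or continue their conventional physiotherapy". The same section opens by saying that "all patients will begin their 12-week physiotherapy (or no-physiotherapy) regimen according to their randomisation".

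Section 7.4.1 has all patients, in both arms, take the insoles home after Baseline for two weeks of monitoring. Sections 7.5.1 and 7.5.4 repeat this after Visits 3 and 4. Section 8.9 collects adverse events of special interest, serious events and device-related events from consent onwards.

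**The concern.** A rule that removes non-starters suits a trial in which the study supplies both treatments. Here it supplies only one. FeetMe patients receive their programme from the sponsor whatever the local provision. Controls must find their own physiotherapist, and the protocol expects that some will not. The rule then acts on access to care in one arm only. A patient without access who is randomised to control would leave the Safety Set, while a similar patient randomised to FeetMe would stay.

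Three things are at stake. First, the safety denominators would no longer be comparable between the arms. Second, controls who wore the insoles at home would be absent from the tables of device-related events, although the insoles are one of the named study devices. Third, a control without access who switches to FeetMe at Week 12 has full exposure to the experimental programme but has still never started the therapy assigned at randomisation. The literal rule removes that patient too, although the synopsis lists device-related and procedure-related events at Week 24 among the endpoints.

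**Working it through.** **Step 1: the plan's own group size.** Section 9.4 uses a difference of 14 cm/s, an SD of 27 cm/s, two-sided alpha 0.05 and 80% power.

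- Normal approximation: n = 2 × (1.960 + 0.842)² × 27² / 14² = 58.4, so 59 per group.
- With the t distribution: 59.4, so 60 per group, as stated.
- With 20% drop-out: 60 / (1 − 0.20) = 75 per group, as stated.

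The sample size reproduces and is not at issue. It supplies the 75 used in Step 3.

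**Step 2: apply the rule to three kinds of patient.**

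| Patient | Wears insoles at home | Literal reading of 9.1 | Reading with no physiotherapy as a regimen |
|---|---|---|---|
| Control who obtains physiotherapy | Yes | In | In |
| Control who never obtains it | Yes | Out | In |
| FeetMe patient with no local access | Yes | In, if the programme is started | In, if the programme is started |

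The two readings differ only in the second row. Section 9.1 does not choose between them. The literal reading rests on the wording of 9.1, the label in Table 9.1 and the access condition in 7.4. The other rests on the opening sentence of 7.4 and the synopsis description of the comparator.

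Neither reading treats the arms alike. Under the literal one, the rule removes controls for lack of access. Under the other, almost every control has started automatically, and the exclusion has practical effect only for FeetMe patients who do not begin.

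**Step 3: possible size under the literal reading.** The protocol gives no share of controls who never start, so the share p is an assumption. Removed controls = 75 × p, with no removals for any other reason.

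| Assumed p | Removed (75 × p) | Controls left | Safety Set total (of 150) |
|---|---|---|---|
| 5% | 3.75, about 4 | about 71 | about 146 |
| 10% | 7.5, about 8 | about 67 | about 142 |
| 20% | 15 | 60 | 135 |
| 33% | 24.75, about 25 | about 50 | about 125 |

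The matching access-related removal in the FeetMe arm is 0 in every row.

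**The case against.** The strongest reply is that the protocol already counts no physiotherapy as part of the control treatment. The synopsis, section 4.5 and the opening of section 7.4 all point that way, and on that view a control without access has begun the assigned regimen and stays in the set. This is a fair reading, and it is why literal exclusion cannot be called certain. It does not settle the matter. No arm is randomised to no physiotherapy, 9.1 does not adopt that reading, and a later sentence in 7.4 makes the start conditional on access. Two analysts could build two different Safety Sets from this text.

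A second reply is that defining a start is a derivation detail for the statistical analysis plan. The plan may well add detail, but the protocol itself fixes the exclusion, and it is this stated rule that conflicts with the stated control arm.

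A third reply is that section 4.7 does not treat the control patients' insoles and Evaluation application as investigational. That weakens the device-exposure argument for controls who never switch. It does not remove the ambiguity, and it does not cover those who move to FeetMe at Week 12.

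Several points on consequence stand in full. Section 9.2.7 puts all safety data in the listings, so a reader who infers that events in these patients would be lost goes too far: they would be missing from tables and denominators only. Safety is an exploratory objective, the tables concentrate on device-related events, and no between-arm safety test is described. Rate of falls is a secondary efficacy endpoint, and section 9.1.1 puts efficacy on the Full Analysis Set.

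**Conclusion.** The point holds as a conflict between passages that should be resolved. On the literal wording, controls who never obtain physiotherapy leave the set used for all safety analyses, although they wore the insoles at home and some may later use FeetMe. On the wording about a no-physiotherapy regimen, they stay.

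The number affected cannot be computed from the protocol. The range of about 4 to 25 of 75 controls rests wholly on assumed shares of 5% to 33%. A reader might take the 33% in section 4.2.1 as the expected share, or go higher. The document does not support this. That figure is an upper value for the French population living in a municipality without a practice, not the share of trial patients who never obtain care. Participants must hold a prescription, some are already in rehabilitation (a stratification factor in section 7.2.1.2), and under section 7.4 those who find a therapist later do start. The conflict exists at any share above zero.

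The effect is confined to safety tables and their denominators. The primary, key secondary and other efficacy analyses are unaffected. It is worth correcting because the rule governs every safety summary and the correction is nearly free.

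**What to change.** Replace the Safety Set sentence in section 9.1 with a rule based on device receipt: all randomised patients who received the insoles. Summarise by randomised arm, and show events that occur after a Week 12 switch under the therapy in use at that time. Receipt of insoles is defined identically in both arms, so membership no longer depends on access to care, and FeetMe patients who took the insoles but did not begin the programme are also kept.

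At minimum, add a sentence stating that no physiotherapy counts as a started control regimen. That removes the conflict for controls, but it leaves an exclusion that can act almost only on the FeetMe arm, and it does not say where events after a switch belong.

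A three-way summary by therapy received (FeetMe, physiotherapy, none) is not needed. It would itself form non-randomised groups selected by access.

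The cost is one or two sentences in 9.1. Sample size, study conduct and the efficacy analyses do not change.

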9.1.1 Usage of the analysis sets

The efficacy analysis will be performed on the FAS. The safety analysis will be performed on the SAF.

Table 9.1 outlines the randomised treatment groups and the analysis sets, for each of efficacy and safety.

Table 9.1 Combination of patient cohorts, patient treatment groups and analysis sets

Randomised treatment group	Efficacy	Safety
Patient group A (conventional physiotherapy)	FAS	SAF
Patient group B (FeetMe Rehabilitation)	FAS	SAF

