	Change from baseline to Week 12 (Visit 3) in Stance Time Variability assessed during the 6MWT.
	Secondary Endpoints
	• Rate of falls at Week 12 based on the results of the falls diary.
	• Change from baseline to Week 12 (Visit 3) in the asymmetry of the swing duration assessed during the 6MWT.
	• Change from baseline to Week 12 (Visit 3) in the Mini-BESTest.
	• Change from baseline to Week 12 (Visit 3) in Unified Parkinson's Disease Rating Scale (MDS-UPDRS) Part III sub-score.
	• Change from baseline to Week 12 (Visit 3) in the results of the Parkinson Disease Questionnaire (PDQ-39).
	Exploratory Endpoints
	• Rate of falls at Week 24 based on the results of the falls diary.
	• Change from Baseline to Week 24 (Visit 4) and from Week 12 (Visit 3) to Week 24 in:
	- Gait velocity (cm/s) assessed during the 6MWT
	- Stance Time Variability assessed during the 6MWT
	- Asymmetry of the swing duration assessed during 6MWT
	- the Mini-BESTest
	- MDS-UPDRS Part III sub-score
	- the results of the PDQ-39
	 Change from Baseline to Week 12 (Visit 3) and to Week 24 (Visit 4) and from Week 12 to Week 24 in the:
	- gait parameters measured by the FeetMe Monitor during the 6MWTs other than ones of the primary and secondary endpoints
	- gait parameters measured by the FeetMe Monitor during remote gait monitoring
	- results of the pain VAS
	- results of the Parkinson Disease Sleep Scale 2 (PDSS2)
	- results of the Clinical and Patient Global Impression of Severity scales (CGI/PGI-S)
	- results of the Clinical and Patient Global Impression of Improvement scales (CGI/PGI-I)
	• results of the MDS-UPDRS I, II and IV sub scores
	• Actual versus prescribed time spent on physiotherapy at Week 12 and Week 24.
· · · · · · · · · · · · · · · · · · ·	

	• Results of the Patient and Investigator satisfaction questionnaire.
	• Number of device and protocol procedure related adverse events at Week 12 and at Week 24.

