6 INVESTIGATIONAL PLAN

6.1 Study design and rationale

This is a multicentre, controlled, randomised in two parallel groups, open label study. The study will enroll 150 patients over approximately 18 months and 6 investigational sites.

Having multiple centres enrolling patients will not only maximise the capacity of recruitment but will allow for the evaluation of differences represented by geographical imbalances in the physiotherapy practices across France.

Patients who are found eligible and consent to participate will be randomised either on the conventional physiotherapy or on the FeetMe arm in a 1:1 ratio. Due to the set-up of the FeetMe program (i.e.: personal follow-up of the patients by an APA and the difference in the device needs between the two groups) and the obvious difference in the treatments, a blinded design is not possible. Nevertheless, the objective nature of the primary and main secondary endpoints measured by digital technology and the patient reported nature of most of the remaining outcome measures minimise any potential biassing effect originating from the open label design. Additionally, the final analysis will be performed by a independent blinded statistician.

The equal allocation of patients is maintained during the Primary Intervention Period (from the Baseline Visit till Visit 3) up to the primary endpoint evaluation at Week 12. It is in line with the duration of the FeetMe rehabilitation program. The program is built based on several regulatory recommendation including the HAS and the WHO and expert opinions suggesting that rehabilitation trainings typically show benefit after ten weeks. Additionally, most of the published data supports this duration together with the list of interventions analysed in the European Physiotherapy Guideline for Parkinson's Disease (Keus et al, 2014) where the median duration of the programs is eight weeks. The timing of the primary endpoint at Week 12 is adopted to this standard duration of an intensive rehabilitation therapy off approximately 3 months.

After the Primary Intervention Period patients will be offered to chose how to proceed i.e.: to continue on their original allocation, to switch arms or to stop treatment. In any case the patients will remain in the study until the week 26 EOS visit. The number of patients on the arms at this point will not be controlled and the data gathered will be exploratory in nature. This design is expected to:

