7.5 Long Term Intervention Period

During Visit 3 patients will be asked whether they want to:

a) continue with their already assigned treatment;

Patients will continue with their respective rehabilitation programs.

b) switch to the other arm;

If patients on the conventional physiotherapy arm would like to start the FeetMe program they will be trained to use the devices and will start their 12 weeks program. Patients of FeetMe group wanting to switch from FeetMe to CPt will need to arrange the care themselves. Patients who switch will have the same visit schedule as during the first three months.

c) discontinue rehabilitation.

If a patient would like to discontinue rehabilitation they will still be asked to remain in the study for further data collection.

7.5.1 Remote Gait Monitoring 2

At the end of Visit 3, all patients will perform a second remote gait monitoring period. All patients will use the insoles remotely while performing their day-to-day activities (including physiotherapy) for 2 weeks. Data will be recorded in standalone mode (without a phone).

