7.5.2 Visits 1.2 and 2.2

Four and eight weeks after Visit 3, that is at week 16 and week 20 from Baseline Visit patients who decided to switch will take part in a virtual remote visit (Visit 1.2 and Visit 2.2 respectively).

Patients will be asked to fill in the following questionnaires:

- PDSS-2
- Pain VAS
- Parkinson Disease Questionnaire, Short Form (PDQ-8).
- 7.5.3 Visit 4

Twelve weeks after Visit 3, that is, at the end of the 12-week Long Term Intervention Period, all patients will participate in an in-clinic visit (Visit 4), where they will perform the same series of assessments as in the Baseline Visit and Visit 3. Patients will need to bring their FeetMe devices, their diaries, trackers and filled-in questionnaires to the visit.

The following assessments will be performed at Visit 4:

- Gait Assessments, which must be performed in the ON-phase:
 - 6 Minutes Walk Tests (6MWT)
 - Mini-BESTest.

During the 6MWT and the Mini-BESTest, patients must wear the insoles. Specific instructions set out in the Site User Manual must be followed when setting up and executing the assessments.

- Disease specific rating scales:
 - MDS-UPDRS
- Other Assessments:
 - FOG-Q
 - PDSS2
 - Pain VAS
 - PDQ39
 - Clinical Global Impression of Improvement / Patient Global Impression of Improvement (CGI/PGI-I)
- Potential adverse events and change in concomitant medication since the last contact.

- The source documents must be collected from the patients and the diary and tracker transcribed into the database.
- At the end of the visit the patients will return home with their devices and proceed into the Remote Gait Monitoring 3 (Section 7.4.4).

7.5.4 Remote Gait Monitoring 3

At the end of Visit 4, all patients will take the FeetMe Insoles with them to their homes. All patients will again use the insoles remotely while performing their day-to-day activities (including physiotherapy) for two weeks. Data will be recorded in standalone mode.

Once the Remote Gait Monitoring 3 period is completed, all patients will return all the FeetMe devices to the site via courier. The site personnel will make sure the data is downloaded as described in the Site User Manual.

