9.2.7 Analysis of safety outcomes

The SAF will be used to perform all safety analyses.

If not otherwise stated, only device-related safety data will be considered in tables and figures. All safety data will be included in listings, with flags for safety data not considered to be treatment emergent.

Device-related AEs and SAEs will be tabulated by patient cohorts, SOC, and preferred terms. The events will also be summarized by maximum intensity, relationship to study treatment and outcome (premature discontinuation from treatment).

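### Safety is grouped by randomised arm although patients may change treatment at Visit 3, so the Week 24 count would place FeetMe-programme events in switched controls under conventional physiotherapy

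*Protocol*

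**What the plan says.** **Grouping.** Section 9.1 defines the safety population by randomisation and start of treatment: "The Safety Set (SAF) includes all subjects who were randomised, removing only patients who do not start their assigned therapy". Section 9.1.1 then says "Table 9.1 outlines the randomised treatment groups and the analysis sets, for each of efficacy and safety". The caption reads "Table 9.1 Combination of patient cohorts, patient treatment groups and analysis sets", but the rows are only group A (conventional physiotherapy) and group B (FeetMe), under a column headed as the randomised group. Section 9.2.7 adds: "Device-related AEs and SAEs will be tabulated by patient cohorts, SOC, and preferred terms".

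**Change of treatment.** Section 6.1 lets patients choose after the primary period "to continue on their original allocation, to switch arms or to stop treatment". Section 7.5 says of controls: "If patients on the conventional physiotherapy arm would like to start the FeetMe program they will be trained to use the devices". They then begin a 12-week programme of their own. FeetMe patients may move to conventional physiotherapy or discontinue rehabilitation and stay in follow-up.

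**Endpoint and window.** The synopsis lists as exploratory: "Number of device and protocol procedure related adverse events at Week 12 and at Week 24". Table 5.1 gives the same endpoint with no time point. Section 8.9 collects the relevant events from consent until participation ends. The only analysis planned specifically for switchers, in section 9.5.3, is descriptive and concerns efficacy.

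**The concern.** The stated safety objective in Table 5.1 is to evaluate the safety of the FeetMe programme. Up to Visit 3 the randomised label and the treatment in use should broadly coincide, so grouping by arm describes that programme. After Visit 3 they can separate in both directions, and the protocol gives no rule for assigning an event to the treatment in use when it occurred.

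A device-related event in a former control now doing FeetMe exercises would therefore appear in the conventional-physiotherapy column. A FeetMe patient who has stopped would remain in the FeetMe column without programme exposure. Both effects shrink the apparent gap between the columns in a Week 24 table. A reader using that table to judge the programme would see too few of its events under its own name.

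**Working it through.** **Step 1: which grouping the text fixes.** Section 9.2.7 says patient cohorts. The term appears elsewhere only in the caption of Table 9.1, whose rows are the two randomised groups. The safety-set definition contains no treatment-received rule, and no other section groups safety by treatment in use or by period. Equating cohorts with randomised groups is thus an inference, but it is the only grouping that the protocol defines.

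**Step 2: which counts are affected.** Switching is decided at Visit 3 (Week 12), so the Week 12 count is untouched. Any count running to Week 24 or beyond is affected.

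**Step 3: size.** The protocol states no figure for this, and section 6.1 says that numbers per arm after Visit 3 are not controlled. The following is therefore illustrative.

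Inputs:
- 75 patients per arm (section 9.4).
- *s*, the share of controls who switch to FeetMe: assumed 20% and 50%.
- *q*, the share of FeetMe patients who leave the programme at Week 12: assumed 10% and 30%.
- One patient-period is one patient on the FeetMe programme for one 12-week period. Losses before Visit 3 are ignored at first.

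Formulas:
- Share of FeetMe users in weeks 12–24 labelled control = 75*s* / [75*s* + 75(1 − *q*)].
- Share of all FeetMe patient-periods to Week 24 labelled control = 75*s* / [75 + 75(1 − *q*) + 75*s*].

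Results:
- *s* = 20%, *q* = 10%: 15 switchers and 67.5 continuing. Weeks 12–24: 15/82.5 = 18%. To Week 24: 15/(75 + 67.5 + 15) = 15/157.5 = 9.5%.
- *s* = 50%, *q* = 30%: 37.5 switchers and 52.5 continuing. Weeks 12–24: 37.5/90 = 42%. To Week 24: 37.5/(75 + 52.5 + 37.5) = 37.5/165 = 22.7%.

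If only 60 per arm reach Visit 3 (the 20% loss used in section 9.4), the weeks 12–24 shares do not change. Counting lost patients as a full first period, the cumulative shares become 12/(75 + 54 + 12) = 8.5% and 30/(75 + 42 + 30) = 20.4%.

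**Step 4: in events.** Suppose, purely for illustration, 0.10 programme-caused events per patient per 12 weeks, *s* = 40% and *q* = 0. The control column receives 75 × 0.40 × 0.10 = 3.0 such events and the FeetMe column 75 × 0.10 + 75 × 0.10 = 15.0, so 3/18 = 16.7% are under the wrong name. The difference per randomised patient is (15 − 3)/75 = 0.16, against 0.20 with no switching. The 16.7% does not depend on the assumed event rate.

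**The case against.** Table 9.1 can be read as saying only which analysis set applies to each arm, with post-switch grouping and exposure denominators left to the SAP. Section 9 does assign data displays and algorithms to the SAP, which was not available here. This tempers the point but does not remove it. The table has a safety column by randomised group, and section 9.2.7 offers no alternative. A SAP that follows the text reproduces the problem, and one that departs from it needs the protocol wording changed.

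The endpoint is also modest: an exploratory number of related events, with no planned safety rate or between-arm test. Section 9.2.7 summarises events by relationship to treatment and lists all safety data, so a switched control's event is not lost. Controls also wear the insoles for monitoring, so some events in their column may belong there. All of this stands and limits the weight of the point.

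Three stronger readings are tempting but not supported:
- *That switching by controls is forecast.* Section 6.1 says that the design offers controls without a therapist an opportunity to switch. It predicts no numbers.
- *That a planned comparison of safety rates is biased.* None is planned. The risk lies in how a descriptive table is read.
- *That events in the last monitoring period are excluded.* After Visit 4, section 7.5.4 says: "All patients will again use the insoles remotely while performing their day-to-day activities (including physiotherapy) for two weeks". The Week 24 limit, however, is synopsis wording only. Table 5.1 has no cut, section 8.9 collects to the end of participation, and all safety data are listed. This is a wording mismatch to reconcile, not a demonstrated loss of data.

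**Conclusion.** The point holds for safety tables that extend past Visit 3. As written, the only defined grouping is the randomised arm, so FeetMe-programme events in switched controls would be tabulated under conventional physiotherapy, and patients who have left FeetMe would remain under FeetMe. Under the assumed 20–50% switching and 10–30% leaving, about 10–23% of FeetMe patient-periods to Week 24 would carry the control label. The 18–42% figure applies to weeks 12–24 alone and should not be quoted for a cumulative Week 24 count. Both ranges rest on assumed rates.

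The Week 12 safety count and the primary efficacy analysis are not affected. The consequence is a misleading exploratory table, worth correcting because describing the programme's safety is a stated objective.

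**What to change.** In sections 9.1.1 and 9.2.7:
- Tabulate safety up to Visit 3 by randomised treatment started.
- From Visit 3 to the End of Study Visit, tabulate by treatment in use at event onset, with at least three categories: FeetMe, conventional physiotherapy, none.
- Show control-to-FeetMe switchers separately, and give the number exposed or the time on FeetMe for each group.
- Define patient cohorts, or replace the term.

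Align the synopsis endpoint with Table 5.1 and with the collection window in section 8.9, so that one cut-off is stated throughout.

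The cost is small. The choice at Visit 3 (section 7.4.3), events to the end of participation (section 8.9) and practice time in the application (section 6.4.2) are already collected. The change is wording plus one more set of descriptive tables. The drawback is that some post-Week 12 groups may be small, so these tables should stay descriptive.
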